## 2.0 Objectives

The goal of the 4-year UH3 implementation phase is to conduct a trial to compare two health care delivery approaches for chronic pain management (Whole Health Team and Primary Care Group Education) and both will be compared to Usual Primary Care in approximately 765 Veterans from 6 geographically diverse VA facilities in order to achieve the following study objectives:

**UH3 Aim 1:** Conduct a multi-site pragmatic trial of Whole Health Team (WHT) vs. Primary Care Group Education (PC-GE) and both compared to Usual Primary Care in veterans with moderate to severe chronic pain. **We hypothesize that WHT will be superior to PC-GE and both will be superior to Usual Primary Care (UPC) with respect to the following outcomes:**

**H1.a.** Improved pain interference (**primary outcome**) and pain intensity, functioning and quality of life (**secondary outcomes**).

**H1.b.** Decreased use of higher-risk pain medications, including opioids or high-risk combinations of pain medications (i.e., co-prescription of opioids and benzodiazepines) (**secondary**).

**H1.c.** Engagement in a greater number of non-pharmacological pain management activities (**secondary**).

**H1.d.** Improvement in mental health-related symptoms, including sleep problems and suicidality (**secondary**).

**UH3 Aim 2:** Conduct a process evaluation of the two active interventions (WHT and PC-GE) and budget impact analysis that includes costs to implement and execute the two active interventions as well as the control condition (UPC), to support the development of an implementation toolkit for scaling and dissemination.

**UH3 Aim 3:** Using a nationwide cohort of veterans, investigate the impact of the COVID pandemic on Veteran subgroups' utilization of non-drug, Whole Health, and CIH services for chronic pain management.

**H3.a.** Racial/ethnic minority veterans' utilization of pain management services may be differentially negatively impacted by the COVID pandemic.

**H3.b.** Women veterans' utilization of pain management services may be differentially negatively impacted by the COVID pandemic.

**H3.c.** Rural veterans' veterans' utilization of non-drug pain management services may be differentially negatively impacted by the COVID pandemic compared to urban-dwelling veterans.

### 3.0 Resources and Personnel

The main aim of this research is to conduct a multi-site pragmatic trial of WHT vs. PC-GE and both compared to Usual Primary Care in approximately 765 veterans with moderate to severe chronic pain, irrespective of the use of long-term opioid therapy across six geographically diverse VA facilities. The study will be based at the San Francisco VA Health Care System (SFVAHCS), the VA Connecticut Healthcare System (VACHS), the VA Portland Health Care System (VAPORHCS), the James A. Haley Veterans Hospital (Tampa VA), and the VA St. Louis Health Care System (VASLHCS). The Central Arkansas Veterans Healthcare System (CAVHS) will serve as a back-up site in the event that we are not meeting our enrollment targets.

### **Memoranda of Understandings (MOUs):**

SFVAHCS holds an MOU with the Northern California Institute for Research and Education (NCIRE), the non-profit affiliate that administers this grant.

## **4.0 Study Design**

We aim to conduct a large-scale pragmatic randomized controlled trial in VA focused on non-pharmacological approaches to pain management and other comorbid conditions. This trial will compare two experimental health care delivery approaches for chronic pain management to each other and also to usual primary care in approximately 765 veterans from 6 geographically diverse VA facilities. **Aim 1** compares Whole Health Team (WHT) and Primary Care Group Education (PC-GE), two distinct patient-centered pain management approaches that differ in structure, comprehensiveness, and intensity. The *more* intensive WHT model employs a Whole Health multi-modal biopsychosocial approach delivered by an interdisciplinary pain team consisting of a primary care provider (PCP), integrative health clinician (e.g. mindfulness instructor) +/- a psychologist. The WHT will use the VA Whole Health Personalized Health Planning and Coaching model to promote wellness in veterans with chronic pain. The *less resource-intensive*, PC-GE adapts Cognitive Behavioral Therapy for Chronic Pain (CBT-CP) for a group format based in primary care. This model consists of psychologist-led weekly group sessions emphasizing pain self-management skill-building, coping techniques and multi-modal nonpharmacologic approaches to pain management. Elements common to both arms include point-of care data capture, and access to a web/mobile Whole Health Resource Directory. Both interventions will be compared to Usual Primary Care in which enrolled patients with chronic pain will be randomized to receive usual primary care. All subjects will be followed for 12 months to complete study assessments at baseline, 3, 6, 9 and 12 months.

We will allow for enrollment up to 800 veterans with moderate to severe chronic pain (irrespective of opioid therapy status), across 6 geographically distinct VA facilities including the medical centers and community-based outpatient clinics. Due to varying rates of recruitment at our six sites, we will continue to enroll until we achieve our target sample size of 765 veterans enrolled. As all our sites are actively recruiting it will be difficult to cut off exactly at 765. Thus, we plan to enroll any veteran who has received a recruitment call while attempting to reach our target sample size of 765 enrolled, allowing for up to 800 veterans. Participants will be randomly assigned at the individual level to either WHT, PC-GE or Usual Primary Care, stratified by site, sex, and use of prescribed opioids for chronic pain. The follow-up period for the three arms will be 12 months. The primary outcome is change in pain interference. Secondary outcomes include change in pain intensity, functioning, quality of life, changes in use of pain medications, including opioids (if applicable) and changes in nonpharmacological pain self-management activities. In addition, change in comorbid mental health-related symptoms (with a focus on sleep and suicidality), will be evaluated. To guide interpretation of trial findings and facilitate future implementation, **Aim 2** will consist of a process evaluation in which we will assess participants' and stakeholders' experiences of the implementation and execution of the two active interventions, as well as relative costs of all three study arms through a budget impact analysis. Aim 2 activities will inform the development of an implementation toolkit for scaling and dissemination.

As the study is during the COVID-19 pandemic, **Aim 3** will be using a nationwide cohort of veterans from the entire VA system, to investigate the differential impact of the COVID pandemic on racial/ethnic minority Veterans' use of Whole Health and CIH services from chronic pain management. (Specifics detailed in Section 15.0)

## 4.1 Implementation-Focused Process Evaluation:

During the 4-year trial, we will conduct a process evaluation of the implementation of the two active interventions (WHT and PC-GE), consisting of patient semi-structured interviews and EBQI meetings with study stakeholders. The overarching goal of the process evaluation is to understand patients', clinicians' and VA leadership's experiences with these interventions and identify strategies to enhance future implementation and dissemination of effective pain care interventions. Specific goals of the process evaluation are fourfold: 1) to increase the relevance of the primary research findings to patients, clinicians and health care decision-makers; 2) to increase the likelihood of timely translation of research findings into diverse practice settings; 3) to generate information to guide interpretation of primary trial findings; and 4) to create an implementation toolkit to support future implementation of study interventions in diverse practice settings.

The process evaluation will start in the second half of the first year of the UH3 trial and conclude in the first half of the final year. Rapid analysis of process evaluation findings will inform iterative improvements to the implementation strategy as the trial progresses. The goal of this rapid learning approach is to ensure that the intervention is aligned with everyday clinical care and the evolving needs for pain management within the VA healthcare system. This in turn will increase the likelihood that the approach is sustained in real-world clinical care settings after the trial has ended. The final trial year will be devoted to both quantitative and qualitative data analysis; dissemination of findings through reports, manuscript, abstracts and cyberseminars; and completion of an implementation toolkit including all study materials and software to support future scale and dissemination activities.

The **RE-AIM (Reach, Effectiveness, Adoption, Implementation, Maintenance) Framework** will guide our process evaluation of the implementation strategy. The table below delineates the methods we will employ to assess each RE-AIM domain: **Reach** represents the proportion of eligible participants that enrolls in the study. **Effectiveness** represents patient-level clinical outcomes of the interventions as pragmatically implemented in routine care settings at each of the sites. Effectiveness will be evaluated through our pragmatic effectiveness trial using the pre-specified outcomes. **Adoption** represents the proportion of VA staff referring participants to the study, as well as adoption of the care delivery strategies (WHT and PC-GE) by the clinical teams based at each of the VA study sites at the end of the study. A more in-depth qualitative understanding of both reach and adoption will be obtained at stakeholder EBQI meetings and through informal ethnographic observation of other key meetings/events associated with study implementation at each site. **Implementation** represents the fidelity with which the interventions are implemented in routine care. Supervision and fidelity monitoring of staff conducting each of the interventions at the study sites will be used to evaluate adoption as well as implementation. In addition, the EBQI meetings with stakeholders will evaluate the acceptability and feasibility of the interventions (as implemented) and specific barriers to and facilitators of implementing the interventions. **Maintenance** represents the degree to which the pain management approach (WHT vs. PC-GE) is likely to be sustained. This dimension will also be assessed during EBQI meetings at the end of the trial.

### RE-AIM Implementation Evaluation: Quantitative & Qualitative Components

Reach (Years 1-2)	
On a quarterly basis, we will monitor:
 
 
• The number of potentially eligible participants contacted
 
• The proportion of participants that enrolls
 
• The percentage of enrolled participants that attends required study-related visits
 

Effectiveness (Years 1-3)	
Effectiveness will be evaluated at the conclusion of this pragmatic trial using pre-specified outcomes.
 
Primary and secondary outcomes to be measured include:
 
 
• Pain interference score (primary)
 
• Pain intensity, functioning and quality of life, decreased use of higher-risk pain medications, engagement in a greater number of non-pharmacological management activities, and improvement in mental health-related symptoms
 
 
Outcomes ascertainment methods and specific measurement instruments are detailed in Section 7.2.4.

Adoption & Implementation (Years 1-2)	
A process evaluation will be conducted to assess acceptability, feasibility, satisfaction, barriers to, and facilitators of implementation, consisting of:
 
 
• Semi-structured interviews with study stakeholders (n=~40-50).
 
• Semi-structured interviews with veterans (n=~40-50)
 
• EBQI meetings with study stakeholders (n=20-30 at each meeting)
 
• Rapid qualitative analysis to identify interview and EBQI themes
 
 
In addition, study staff fidelity to the interventions will be monitored via:
 
 
• Monitoring staff attendance rates for monthly case conference calls with WHT & PC-GE providers
 
• Conducting ethnographic observation during monthly WHT/PC-GE/Coach provider calls
 
• Auditing clinic notes
 
• Reviewing audio-recorded coaching sessions (5-10% across sites)
 

Maintenance (Years 3-4)	Through ethnographic observation and rapid analysis of stakeholder EBQI meetings conducted at the end of the trial, the likelihood that each pain management approach (WHT and PC-GE) will be sustained will be assessed, and we will identify potential barriers to and facilitators of sustainment.
--------------------------------	---

**1. Qualitative data collection with study stakeholders and clinical interventionists:** The RE-AIM framework will guide qualitative data collection during the process evaluation. We plan to interview a purposive sample of stakeholders and clinical interventionists across all sites, anticipating that we will reach thematic saturation through interviews with 4-6 participants at each site for a post-implementation timeframe (i.e., 18-24 months after intervention launch at each site; n~40-50 interviews). These interviews will be rapidly analyzed, and salient themes will be distilled for the EBQI meetings that follow each round of interviews. We will potentially also collect ethnographic data from monthly national clinician meetings. During the COVID-19 era, semi-structured qualitative interviews with veterans and clinicians will also include a supplemental addendum addressing experiences with care during COVID-19.

Following each round of VA staff and veteran participant interviews, we will conduct an EBQI meeting with study stakeholders, including study clinicians, VA leadership, non-study clinicians and veteran study participants. The EBQI meetings will be led by one of the study PIs, the site PI, a senior member of the qualitative team, and another qualitative investigator to observe and take detailed notes. The EBQI meetings will draw on information gleaned from completed stakeholder and veteran interviews to recap trial progress at the individual sites and pose several discussion questions related to the sites' unique implementation strategy, including acceptability and feasibility of recruitment and enrollment as well as delivery of the pain management interventions (WHT and PC-GE) within each site's clinical settings. The second EBQI meeting will also focus on the potential for long-term sustainability, including barriers and facilitators to widespread dissemination and scale-up at the study site and other VAs.

**2. Qualitative data collection with veterans:** Veteran participants in both the WHT and PC-GE intervention arms will be interviewed by telephone at a single timepoint between study enrollment and the end of their study participation. We will purposively sample diverse participants to maximize participant diversity with respect to age, sex, race/ethnicity, study site, and level of participation in the intervention (defined by the number of intervention visits completed over the first 6 months). Semi-structured interview questions will address experiences with the WHT or PC-GE intervention, perceptions of the value and convenience of the intervention, what (if any) aspects of the intervention influenced their personal treatment outcomes, and any recommendations for improvements. We will continue to conduct interviews with patients until thematic saturation is reached. Based on recommendations for qualitative sampling, we expect to conduct 15-20 interviews for each study arm, for a total of 40-50 participant interviews.

**3. Qualitative data analysis:** Data from all interview transcripts and EBQI meeting field notes will be analyzed by the qualitative research team using rapid analysis methods developed for health services research. At least two trained analysts will independently listen to each interview, read each ethnographic note set, and prepare a written summary using a templated matrix organized by topical areas. The analysts will then collaborate with the investigators to review all matrices, identify recurring themes, and refine the description of each theme for each relevant RE-AIM domain. Identified themes will form the basis of qualitative summary reports and will inform the development of implementation toolkit.

## **4.2 Budget Impact Analysis (BIA)**

BIA has become the standard for developing the business case for healthcare implementation decisions because it provides a straightforward economic comparison of different interventions. In collaboration with the Coordinating Center, [name] will direct the BIA for this study. Results from this BIA will be included as part of the implementation toolkit and will inform future implementation and dissemination efforts.

Costs will be collected for each of the three arms of the study (WHT, PC-GE, Usual Primary Care). Relevant costs can broadly be classified as implementation costs, intervention costs, and other healthcare costs. Implementation costs will be zero for Usual Primary Care, but there will be implementation costs for the two active interventions (WHT and PC-GE), which include staff time for intervention development activities, qualitative assessments for implementation readiness, EBQI activities and training of clinical and intervention staff at each of the enrollment sites. The calculation of costs for implementation of the interventions will require primary data collection.

In addition to health services utilization costs associated with Usual Primary Care (UPC) for chronic pain, intervention costs in this arm will be minimal but will include training of UPC veteran participants and primary care staff on use of the Whole Health Resource Directory. For the WHT and PC-GE interventions, intervention costs will be calculated using a combination of VA administrative and clinical staff time devoted to each of the active interventions as well as costs associated with participant services utilization. Specifically, for the WHT intervention, visit costs will include team conferencing time and clinician time, including coach time (hourly rate for each team member) that will be ascertained using clinic visit notes in the electronic medical record (EMR) plus estimated administrative time for each clinical visit. PC-GE intervention costs will be estimated by accounting for the number of PC-GE modules for patient participants per site and the clinician and administrative time associated with each module. All other VA and non-VA community care healthcare costs will be collected using Decision Support Systems (DSS) National Data Extracts, the official cost managerial accounting system for VHA as well as new databases for computing costs for non-VA community care (after the Mission Act). These analyses will focus on VA and non-VA outpatient visits and outpatient pharmacy costs. Outpatient costs for the main analysis will be organized in the following groups by stop code field: integrative (CIH), primary care, emergency department, mental health, substance use disorder care, specialty pain care, ancillary, physical health specialty, and other. Outpatient VA medication costs will also be assessed using VA DSS data and will be divided by medication

class into opioid, non-opioid pain related, and other. We will also track inpatient admissions of all study participants during follow-up.

The BIA will be conducted in accordance with guidelines from the International Society for Pharmacoeconomics and Outcomes Research. To estimate the budget impact of each intervention relative to UPC we will conduct two analyses, i.e. UPC versus WHT and UPC versus PC-GE. For each analysis, we will estimate the total 12-month cost that would be incurred by VA to implement and deliver the intervention to all patients eligible for the trial relative to UPC. The BIA covariates will be the same as those used in the primary analysis (including sociodemographic characteristics, enrollment site, use of long-term opioid therapy, other pain medication use, presence of comorbid mental health symptoms, baseline pain intensity and interference) plus one-year pre-intervention healthcare utilization costs to control for baseline cost differences. Because healthcare costs are likely to be non-normally distributed, we will use generalized linear models to estimate the effect of each intervention on total costs. To calculate the incremental treatment effect on costs, we will compute two predicted costs for each participant. The first cost prediction will be for costs as though the patient had been randomized to the relevant intervention arm and the second cost prediction will be for costs as if the participant had received UPC. The difference between these two cost predictions represents the potential additional cost of the intervention for the participant because all covariate effects will be identical. Individual cost differences will then be averaged to provide an estimate of the cost to provide the relevant intervention to an average patient at an average site relative to UPC.

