**Table 1. Plan for recruitment of an adequate sample**

Total number of patients expected to be screened	~ 5,464
Of those screened, total number expected to be eligible:	~ 3,825
Target sample size:	~ 765

Compared to the general U.S. population, women are underrepresented in veteran samples. Thus, to achieve better representation of women in the pragmatic trial, we will oversample women by inviting *all* preliminarily eligible women and only a proportion of preliminarily eligible men. If estimated enrollment rates are accurate, we would then enroll women at approximately twice the rate of their prevalence in the veteran population. We will monitor enrollment of ethnic minority participants and if lower than that represented in the veteran population, we will prioritize recruitment of ethnic minorities. Historically, we have found it challenging to recruit veterans prescribed opioids for chronic pain into research studies of alternative management interventions. We will thus also over-sample veterans prescribed opioids.

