### Randomization

After obtaining written consent and completing the baseline interview, the local site coordinator will initiate randomization using the study application randomization form. For those who sign the IC document and mail back the forms, the study coordinator will wait until the written consent form is received before randomizing the patient to a study arms. The randomization code will not be visible to personnel conducting randomization and can be completed only once per study ID, preventing study personnel from influencing treatment allocation. This process will simultaneously inform the coordinator and participant of the primary study arm assignment.

- The unit of randomization is the patient. After eligible and interested patients complete a written informed consent, each site will randomize enrolled patients to WHT, PC-GE, or

Usual Primary Care in permuted blocks of 24 and 48, stratified by site, prescription opioid use (yes/no) and sex. We will oversample women veterans, aiming for roughly 20% at each site. Because the sample size computation was based on 2 types of pairwise comparisons with different pre-specified effect sizes and alpha levels, the numbers of patients are different across intervention arms. The enrollment period is approximately 24-30 months: The target enrollment for each site is 17 patients in the UPC arm, 69 in the WHT arm and 69 in the PC-GE arm over the duration of the enrollment period.

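### The budget impact analysis targets all trial-eligible patients but averages, unweighted, over a sample whose sex and opioid mix was altered by design

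*Protocol*

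**What the plan says.** Protocol 4.2 states the target. For each active arm against usual primary care (UPC), the analysis will "estimate the total 12-month cost that would be incurred by VA to implement and deliver the intervention to all patients eligible for the trial".

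The estimator follows in the same paragraph. For the cost model, "we will use generalized linear models to estimate the effect of each intervention on total costs"; the link, the distribution and any treatment-by-covariate interactions are not given. Then "we will compute two predicted costs for each participant", one under the intervention and one under UPC, and finally: "Individual cost differences will then be averaged to provide an estimate of the cost to provide the relevant intervention to an average patient". Sociodemographic characteristics, site and long-term opioid therapy are among the covariates.

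Protocol 5.3 (text under Table 1) describes the sampling. All preliminarily eligible women are invited but only some of the men, and if enrolment goes as expected "we would then enroll women at approximately twice the rate of their prevalence in the veteran population". On opioids: "We will thus also over-sample veterans prescribed opioids". Protocol 8.2 (Randomization) repeats the sex target: "We will oversample women veterans, aiming for roughly 20% at each site".

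No section weights or standardises the cost average to the eligible population. The SAP is confined to Aim 1, so 4.2 is the only plan for this analysis.

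**The concern.** The target and the averaging set are different populations. The target is everyone eligible. The average is taken over those enrolled, whose mix was moved on purpose.

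Covariate adjustment does not close this gap. Having sex and opioid therapy in the model sharpens the contrast between arms, but the predictions are still averaged over the enrolled mix. Whenever the predicted dollar difference varies between people, its mean depends on who is in the average. The plan itself allows for variation: computing a separate difference for each participant is needed only if the differences are not all the same.

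At stake is the economic result of Aim 2, which goes into the implementation toolkit and is meant to inform wider roll-out. An error from sample mix does not shrink as the sample grows. The SAP synopsis records 769 participants already enrolled, so the mix can now be handled only in the analysis.

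**Working it through.** **Is there a figure to reproduce?** Section 4.2 gives no per-patient cost, no total and no count of eligible patients. The adjacent recruitment figures in Protocol 5.3 do reproduce: 765 / 0.20 = 3,825 eligible, and 3,825 / 0.70 = 5,464 screened.

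**Inputs**
- Share of women in the sample, s = 0.20 (Protocol 8.2).
- Share of women in the target, t = 0.20 / 2 = 0.10, implied by the roughly twofold enrolment in Protocol 5.3. This benchmark describes veterans generally, not eligible chronic-pain patients.
- r = incremental cost in the over-sampled group divided by that in the rest. The documents give none, so r is an assumption.

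**Formula.** With a log link and no interaction, a participant's predicted difference is (predicted UPC cost) x (cost ratio of intervention to UPC - 1). It is therefore proportional to predicted UPC cost, even if the intervention-to-UPC ratio is the same for everyone. With two groups,

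relative error = [1 + s(r - 1)] / [1 + t(r - 1)] - 1.

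The same expression applies if interactions make the dollar difference vary, with r the ratio of those differences. With an identity link and no interaction r = 1, and the error is exactly 0.

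**Women, s = 0.20 and t = 0.10**

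| Assumed r | Calculation | Error in the mean |
|---|---|---|
| 0.8 | 0.96 / 0.98 - 1 | -2.0% |
| 1.0 | 1.00 / 1.00 - 1 | 0% |
| 1.2 | 1.04 / 1.02 - 1 | +2.0% |
| 1.5 | 1.10 / 1.05 - 1 | +4.8% |
| 2.0 | 1.20 / 1.10 - 1 | +9.1% |

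**Opioid users.** Neither the target share nor the enrolled share is given. The cases below show only that the sign is open; they are not estimates.

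| Assumed share, target to sample | r = 1.2 | r = 1.5 | r = 2.0 |
|---|---|---|---|
| 20% to 40% | +3.8% | +9.1% | +16.7% |
| 20% to 30% | +1.9% | +4.5% | +8.3% |
| 30% to 30% | 0% | 0% | 0% |
| 30% to 25% | -0.9% | -2.2% | -3.8% |

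**The case against.** The strongest reply is that the bias is conditional and probably small. It needs incremental cost to differ by sex or opioid use, and no section says that it does. The planned visits, coaching sessions and group modules are the same whatever the participant's sex or opioid status, and they are costed by staff time. Sampling error may also dominate. With 341 against 83 patients, and assuming a cost coefficient of variation of 1 and an increment of 20% of mean cost, the standard error is sqrt(1/341 + 1/83) / 0.20, or about 61% of the increment. Much of this stands, and it limits the size of the point. It does not remove the mismatch. The model covers total costs, not only intervention contacts. Hypothesis H1.b expects reduced use of opioids, and savings from cutting existing opioid use can arise only in users. Nor does imprecision excuse averaging over a different population from the one named.

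Three stronger readings are tempting and are not supported.

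- A reader might infer that the sample is enriched for opioid users. Protocol 5.3 gives the reason for over-sampling them: they have been hard to recruit. The effort may only offset low uptake, or fall short of it.
- A reader might infer that the cost figures are simply wrong or too high. The sign depends on unstated cost ratios, and the error can be zero.
- A reader might put a dollar total on the error by applying the 70% eligibility yield to the roughly 60,000 records in Protocol 7.2.1. Those are records to be accessed for recruitment, whereas the 70% applies to patients screened. Section 4.2 also does not say how the mean becomes a total.

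The phrase about all eligible patients is itself undefined. If it meant only the 3,825 screened and eligible, that pool already over-represents women, because only some men are invited, and the mismatch would shrink or vanish. That is a reason to define the term.

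**Conclusion.** The mismatch holds on the text: the analysis names all eligible patients as its target and plans an unweighted mean over a deliberately non-proportional sample. If incremental cost varies by sex or opioid use, that mean is biased for the stated target.

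For women alone the error is about -2% to +9%. This rests on a 20% against 10% share and assumed cost ratios of 0.8 to 2.0. It is zero if the dollar difference is constant. The opioid contribution can be neither signed nor sized from the documents. Confidence is high in the mismatch and low in its magnitude. This is a secondary aim and the likely error is modest, but the correction is cheap enough to make before the cost analysis is run.

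**What to change.** In Protocol 4.2:

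1. Define the eligible population meant by the target, and give its count and how the total is obtained from the per-patient figure.
2. State the link of the generalized linear model and any treatment-by-covariate interactions.
3. Replace the plain mean with a mean of the predicted differences weighted to the sex-by-opioid-by-site distribution of the candidate pool identified from VA administrative data. These are the randomisation strata.
4. State that this pool only approximates eligibility, because the PEG and telephone screening criteria are not applied there.
5. Report the unweighted trial-sample mean alongside.

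The cost is about one paragraph of text, using data already drawn for recruitment, and slightly wider intervals from weighting. Weighting on these strata does not correct for self-selection: only about 20% of eligible patients are expected to enrol. That limit should be stated with the result.
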